1.2.1. Preclinical Studies

The safety pharmacology and toxicology of ALN-PCSSC was evaluated in a series of in vitro and in vivo nonclinical studies.

The drug substance in ALN-PCSSC (ALN-60212) is designed to match the human and cynomolgus monkey mRNA transcripts for PCSK9, sharing a substantial partial match to the rat PCSK9 mRNA. ALN-60212 was informatically identified from a large collection of possible siRNAs targeting PCSK9 based on its predicted potency and selectivity. ALN-PCSSC reduced the expression of PCSK9 in Hep3B liver cells with a median inhibitory concentration of 20 pM and inhibited hPCSK9 serum protein levels in a transgenic mouse model with a single dose effective dose causing 50% inhibition of approximately 2 mg/kg and an effective dose causing 80% inhibition of approximately 6 mg/kg. In single- and multi-dose regimen studies in cynomolgus monkeys, ALN-PCSSC exhibited dose-dependent sustainable suppression of PCSK9 protein that was paralleled by lowering of serum LDL-C with the same kinetics. The time to reach PCSK9 and LDL-C nadir was approximately 20 days and there was no difference in time to nadir between different dose levels. In single-dose studies, the maximal mean PCSK9 and LDL-C inhibition was 85% and 68%, respectively, which was observed at the two highest doses of ALN-PCSSC administered (6 and 10 mg/kg); however, the duration of PCSK9 silencing and LDL-C lowering was markedly extended at the higher 10 mg/kg dose. In multi-dose studies, the maximal mean PCSK9 and LDL-C inhibition was 93% and 74%, respectively, which was similar to that observed in the single-dose study. Following discontinuation of ALN-PCSSC administration, recovery of PCSK9 levels was slow, returning to baseline after 100 days in the single-dose study and only showing partial recovery between doses in the multi-dose regimen. There were no ALN-PCSSC-related changes to the levels of high-density lipoprotein cholesterol (HDL-C) or triglycerides in any of the groups. As expected, total cholesterol levels were reduced by up to 30% reflecting the decrease in LDL-C.

Good Laboratory Practices (GLP) compliant repeat-dose studies of 4 and 15 weeks duration have been conducted in rats and monkeys. These studies included toxicokinetic analysis of ALN-PCSSC in plasma and in tissues, including the liver which is the target organ and the kidney which is the main organ of elimination. The GLP 4-week toxicology studies in rats and

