3.4. Secondary Endpoints

The secondary endpoints of this trial are:

- Percentage change in LDL-C from baseline to Day 90
- Percentage change in LDL-C from baseline to Days 14, 30, 60, 104, 120, 150, and 210
- Proportion of subjects in each group with LDL-C greater than 80% of the baseline value at Day 180 and Day 210
- Duration of time on treatment for subjects to return to 80% of baseline or greater LDL-C or PCSK9 protein
- Individual responsiveness defined as the number of subjects reaching on treatment LDL-C levels of <25 mg/dL, <50 mg/dL, <70 mg/dL, and <100 mg/dL at Days 90, 120, and 180
- Proportion of subjects in each group with greater or equal to 50% LDL-C reduction from baseline at Days 90, 120, and 180
- Percentage change in PCSK9 levels from baseline to Days 14, 30, 60, 90, 104, 120, 150, 180, and 210
- Percentage change in other lipids, lipoproteins, apolipoproteins from baseline at each subsequent visit to Day 210

- Proportion of subjects in each group who attain global lipid modification targets for their level of ASCVD risk

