6.7. Additional Follow-Up Visits (Day 240 to Day 360)

Subjects in whom LDL-C levels have not returned to >80% of baseline values will return monthly (± 3 days) for Follow-Up Visits 10 to 14 (Days 240, 270, 300, 330, and 360) either until this level has been reached or until Day 360. The following procedures will be performed at these visits:

- HbA1c: At Day 270 and Day 360 (central)
- Central clinical laboratory (hematology, chemistry [including fasting glucose, liver and renal function, hsCRP and inflammatory markers IL6, IFN- γ and TNF- α], and coagulation testing)
- ADA at the last visit(central)
- Lipids/lipoproteins (LDL-C, HDL-C, total cholesterol, triglycerides) and PCSK9; non-HDL-C and very low-density lipoprotein-cholesterol [VLDL-C] will be derived from the lipid panel (central)
- Pregnancy test (local) at each additional follow-up visit until LDL-C has returned to > 80% of baseline values
- Concomitant medications

- AE reporting
- SAE reporting

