10.3.3. Analysis Windows and Baseline

The observational period for each subject includes the screening period (from Day -14 to Day -1), the EOS visit (Day 210 or withdrawal date). The time at which LDL-C levels have returned to >80% of baseline values will be the last observation. Any lab results collected after the last observation will not be included in the planned efficacy analysis. Safety events after the last observation, even if collected on the eCRF, will not be included in the planned statistical analysis. However, all data, including that reported after the defined observational period, will be included in the subject data listings.

Unless otherwise specified, for evaluations that are collected at multiple occasions prior to initiation of study drug, the last evaluation will be considered the "Baseline" evaluation for analysis.

Two samples for lipids and PCSK9 will be taken prior to initiation of study drug (one at screening and one prior to randomization on Day 1). The average value of the two samples will be used as the baseline evaluation.

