10.3.4. Missing Data Handling

Unless otherwise specified, missing data will not be imputed and will be excluded from the associated analysis.

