5.3.3. Analysis Windows and Baseline

The observational period for the study includes screening period (from Day -14 to Day -1) to the EOS visit (follow-up Visit 8, Day 210 or withdrawal date). The time at which LDL-C levels have returned to >80% of baseline values will be the last observation. Any lab results collected after the last observation will not be included in the planned efficacy analysis. Safety events after the last observation, if collected on the eCRF, will not be included in the planned statistical analysis. However, all data, including safety events that were reported after the defined observational period, will be included in the subject data listings.

Unless otherwise specified, for evaluations that are collected at multiple occasions prior to initiation of study drug, the last evaluation will be considered the "Baseline" evaluation for analysis. Two PD samples for lipids and PCSK9 will be taken prior to initiation of study drug. The average of the two samples will be used as the baseline evaluation. If only one sample was collected, the collected sample will be used as baseline. If more than two samples were taken, then the average of the last two will be used as baseline.

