5.4.4.2. Endpoints

The secondary endpoints of this trial are:

- Change from Baseline LDL-C
 - Percentage change in LDL-C from baseline to Day 90
 - Percentage change in LDL-C from baseline to Days 14, 30, 60, 120, 150, and 210
 - Proportion of subjects in each group with LDL-C greater than 80% of the baseline value at Day 180 and Day 210
 - Duration of time on treatment for subjects to return to >80% of baseline or greater LDL-C or PCSK9 protein (if not resolved by Day 210, subjects will continue to be followed until LDL-C returns to within 80% of baseline.
 - Individual responsiveness defined as the number of subjects reaching on treatment LDL-C levels of <25 mg/dL, <50 mg/dL, <70 mg/dL, and <100 mg/dL at Days 90, 120, and 180
 - Proportion of subjects in each group with greater or equal to 50% LDL C reduction from baseline at Days 90, 120, and 180
 - Proportion of subjects in each group who attain global lipid modification targets for their level of ASCVD risk

> Change from Baseline Lipids/Lipoproteins

Secondary efficacy assessments will include the measure the effects of ALN-PCSSC on levels of lipids and lipoproteins including total cholesterol, triglycerides, LDL-C (calculated and BQ) HDL-C, non-HDL-C, very low-density lipoprotein (VLDL), Apo-AI, Apo-B, Lp(a), CRP, and PCSK9.

- Percentage change in PCSK9 levels from baseline to Days 14, 30, 60, 90, 120, 150, 180, and 210
- Percentage change in other lipids, lipoproteins, apolipoproteins from baseline at each subsequent visit to Day 210

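### If PCSK9 duration is summarised as its own time, the LDL-C-based follow-up and lab cut-off, with missing values excluded, bias it short

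*Protocol*

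**What the plan says.** **Endpoint.** Protocol 3.4 lists "Duration of time on treatment for subjects to return to 80% of baseline or greater LDL-C or PCSK9 protein". SAP 5.4.4.2 carries the same endpoint and adds that, if there is no return by Day 210, "subjects will continue to be followed until LDL-C returns to within 80% of baseline".

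**Follow-up.** PCSK9 is drawn at every scheduled visit to Day 210 in all subjects (Protocol Table 3). Only subjects whose LDL-C is not yet above 80% of baseline go on to the monthly visits from Day 240, and they stay "either until this level has been reached or until Day 360" (Protocol 6.7). PCSK9 is measured at those visits, but it plays no part in deciding who attends them.

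**Cut-off.** Protocol 10.3.3 states: "The time at which LDL-C levels have returned to >80% of baseline values will be the last observation". SAP 5.3.3 has the same rule and continues: "Any lab results collected after the last observation will not be included in the planned efficacy analysis".

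**Missing data.** Protocol 10.3.4 and SAP 5.3.4 say that, unless otherwise specified, "missing data will not be imputed and will be excluded from the associated analysis". Neither document specifies otherwise for the duration endpoint, and neither gives it a censoring rule or a time-to-event method.

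**Status.** The protocol synopsis makes the secondary analyses descriptive.

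**The concern.** The endpoint names two markers, and the rules that end observation look at one. A subject whose LDL-C has returned and whose PCSK9 has not gets no further visits after Day 210. Under the default missing-data rule that subject has no PCSK9 duration and drops out of the summary. Those who remain are the subjects whose PCSK9 returned no later than the exit visit, so the summary is short by selection, and by an amount that can differ between arms. SAP 5.4.4 says the efficacy and safety results will help determine the Phase III dose. A PCSK9 duration by arm could be read in that light.

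**Working it through.** **1. Observation window.** 14 days of screening plus 360 gives 374 days, and 14 plus 210 gives 224 days. Both match Protocol 6.

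**2. Who is lost, from the rules alone.**

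| LDL-C first above 80% | PCSK9 drawn afterwards? | Used in the efficacy analysis? |
|---|---|---|
| Before Day 210 | Yes, to Day 210 | No, if the cut-off is applied literally |
| Day 210 or later | No | Nothing to use |
| Not by Day 360 | Followed to Day 360 | Yes |

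The second row is the firm loss. The first depends on a literal cut-off. Applied that way, the rule would also delete Day 180 primary values in subjects who recover early, so it is doubtful that it is meant.

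**3. Expected order.** Protocol 1.2.1 reports for monkeys given a single dose that "the maximal mean PCSK9 and LDL-C inhibition was 85% and 68%, respectively", with "suppression of PCSK9 protein that was paralleled by lowering of serum LDL-C with the same kinetics". The multi-dose maxima are 93% and 74%. If both markers recover by the same fraction at the same time, then when LDL-C is 20% below baseline:

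- single dose: PCSK9 = 1 − 0.85 × 0.20/0.68 = 75.0% of baseline
- multi-dose: PCSK9 = 1 − 0.93 × 0.20/0.74 = 74.9%

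The LDL-C to PCSK9 ratio is 68/85 = 0.80 and 74/93 = 0.80. Ratios of 0.7 and 1.0 put PCSK9 at 1 − 0.20/0.7 = 71% and 1 − 0.20/1.0 = 80%. The documents give no human PCSK9 values.

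**4. Length of the lag.** Two rough routes:

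- Monkey depths, nadir assumed at Day 84, LDL-C crossing at Day 210 (126 days later). Exponential recovery: ln(0.85/0.2)/ln(0.68/0.2) = 1.18, a lag of 23 days. Linear recovery: (1 − 0.2/0.85)/(1 − 0.2/0.68) = 1.08, a lag of 10 days.
- Phase I LDL-C figures: group nadirs of 50% to 59% (Protocol 1.3.2), taken at Day 84, and about 40% at Day 140 (Protocol 1.2.2). Half-life of effect = 56/log2(nadir/40): 174 days for 50%, 122 for 55%, 100 for 59%. With ratio 0.8, lag = half-life × log2(1/0.8) = 56, 39 and 32 days.

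The lag is about 10 to 56 days, so PCSK9 return usually falls one or two monthly visits after exit.

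**5. Illustrative simulation.** 200,000 subjects; exponential recovery from a Day 84 nadir; visits every 30 days to Day 360; baseline the mean of two samples. Assumed: nadir SD 8 points, half-life log-SD 0.3, ratio log-SD 0.1, within-subject log-SD 0.08 (LDL-C) and 0.10 (PCSK9). Exit is the first visit with LDL-C above 80%, and every PCSK9 value to Day 210 is counted.

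| Single-dose setting | PCSK9 return unseen among LDL-C exits | Shortfall in observed mean |
|---|---|---|
| Base: nadir 55%, ratio 0.8 | 58% | 26 days |
| Nadir 50% / 59% | 65% / 53% | 23 / 28 days |
| Ratio 0.7 / 0.9 / 1.0 | 70% / 46% / 36% | 30 / 23 / 20 days |
| More noise (0.10 and 0.20, ratio log-SD 0.2) | 44% | 29 days |
| No measurement noise | 83% | 45 days |

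In the base case 91% exit on LDL-C by Day 360, and 0.91 × 0.58 × 60 = 32 of 60 have no observed PCSK9 return. PCSK9 return is seen in 43%, against 81% with sampling to Day 360. The mean among observed returns is 245 days against 271. With the cut-off applied literally, 62% of exits are unseen.

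For two-dose arms (curve shifted 90 days), 64% exit and 69% of those are unseen. The mean shortfall is only about 8 days, because the Day 360 limit hides many returns in any case.

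**6. Kaplan-Meier median**, censored at the last PCSK9 sample against full sampling to Day 360: 300 and 300 days in the base case, 360 and 330 with nadir 50%, 360 and 300 with ratio 0.7, not reached and 300 without noise.

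**The case against.** The strongest reply is that the endpoint is a single item joined by the word or. Read as whichever marker returns first, it is fully observed under the present rules and nothing is lost. That stands as a possible reading, but neither document states it.

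Second, the stated objective (Protocol 2.2) is the duration of lipid-lowering effect, and PCSK9 is not a lipid. Its own objective, levels over time, is met by the percentage changes to Day 210. This also stands. A reader might infer that the plan fails a stated objective on PCSK9 duration; the documents contain no such objective.

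Third, a reader might infer that a PCSK9 return can be recorded only if it comes no later than that of LDL-C, in every treated subject. That is too strong. PCSK9 is drawn to Day 210 whatever the LDL-C, so a subject with LDL-C back at Day 150 and PCSK9 back at Day 180 has both recorded unless the cut-off is taken literally.

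Fourth, the order and the sizes are inference. The 0.80 ratio comes from mean maxima in monkeys, and its use near baseline in humans is assumed. The half-life joins nadirs at doses of 300 mg or more to a Day 140 figure whose dose group is not given. Phase I puts the maximum by Day 84, not at it. With the nadir at Day 30, LDL-C exits fall from 91% to 62%, and PCSK9 return is seen in 27% against 44% with sampling to Day 360. At ratio 1.0, with no expected lag, 36% are still unseen, so part of the 58% is assumed noise. The figures are illustrative.

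Last, no one has specified an observed-only mean. True, but exclusion is the written default, and nothing replaces it for this endpoint.

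**Conclusion.** The point holds conditionally. If PCSK9 duration is reported as its own time, the exit rule, the lab cut-off and the exclusion of missing values together bias it short. The firm loss is in subjects whose LDL-C returns at Day 210 or later. That this is the usual order rests on the monkey ratio and on both markers sharing one recovery curve. On those assumptions, about half or more of single-dose subjects leaving on LDL-C could lack an observed PCSK9 return, with an observed mean some three to six weeks short. Both sizes are illustrative and not forecasts for this trial.

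The documents do not support reading this as a threat to the primary result or as proof that longer follow-up is needed. The endpoint is secondary and descriptive. The Day 180 comparison, the LDL-C duration and the PCSK9 percentage-change endpoints are not the subject of this point. The extension is a separate, optional study and does not supply this endpoint. This is a cheap improvement.

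**What to change.** - **Protocol 10.3.3 and SAP 5.3.3:** exempt PCSK9 from the LDL-C cut-off, so that every PCSK9 value drawn is used.
- **SAP 5.4.4.2:** define LDL-C and PCSK9 durations as two separate times. Censor a subject with no observed PCSK9 return at the last PCSK9 sample, in place of exclusion. Give Kaplan-Meier summaries by arm with the number censored at LDL-C exit, and state that this censoring is informative.
- **Or** delete PCSK9 from the duration endpoint in both documents, since percentage change to Day 210 already describes it. If the sponsor means whichever marker returns first, saying so is enough.

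The cost is two or three sentences and a little more analysis, with no new visits or assays. Censoring does not cure everything. Subjects who leave on LDL-C are likely to be close to PCSK9 return, so the Kaplan-Meier estimate can run long (step 6), which is why the number censored at exit must be shown.

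Extending follow-up until both markers return is a trade-off and is not required. It would add about 180 × 1.13 + 180 × 0.61 = 313 visits on the assumptions above and delay entry to the extension.

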7. PROTOCOL ASSESSMENTS

7.1. Assessment of Safety

7.1.1. Adverse Events

Subjects will be carefully monitored for AEs by the investigator during the designated study period (see [Section 8](#) for details).

7.1.2. Clinical Laboratory Assessments

Specimens will be obtained at the time points in the Schedule of Assessments ([Table 3](#)). Additional aliquots of plasma or serum will be collected at each time point and stored for any clinically indicated efficacy or safety analyses to be conducted at the end of the study.

Subjects will be in a fasted state for all clinical laboratory assessments. Screening lab tests as detailed in the Schedule of Assessments and [Section 6.3](#) will be performed by each participating institution's laboratory ([Appendix C](#)). Results from these screening tests must be available before the start of study drug injection on Day 1 to confirm subjects meet eligibility criteria. Details regarding the processing, shipping, and analysis of samples will be provided in the Laboratory Manual. Note: Efficacy laboratory assessments (eg, LDL-C and PCSK9) are described in [Section 7.2](#).

Laboratory assessments may include:

Hematology: hemoglobin, hematocrit, erythrocytes, reticulocytes, platelet counts, mean cell hemoglobin, mean corpuscular volume, mean corpuscular hemoglobin concentration, white blood cell count, differential blood count.

Coagulation: prothrombin time (PT), international normalized ratio (INR), activated partial thromboplastin (aPTT). Blood samples for determination of coagulation parameters will be performed prior to start of study drug injection on Day 1.

Biochemistry: AST, ALT, alkaline phosphatase, gamma glutamyl transferase, uric acid, total bilirubin, sodium, creatine phosphokinase, albumin, total protein urea (BUN), creatinine, potassium, chloride, glucose (fasting), HbA1c, inorganic phosphate, hsCRP (fasting), eGFR, calcium, tryptase (as required), and inflammatory markers IL6, IFN- γ and TNF- α .

Urinalysis: Urinalysis will be performed at the time points defined in the Schedule of Assessments and evaluated by dipstick analyses at the investigational site local lab (a standardized dipstick test will be supplied by the Central Laboratory). Urinalysis will be performed from a sample of mid-stream urine. In case of abnormal results, microscopy and other assessments will be performed at the local lab. The following parameters will be assessed: Nitrite, protein, glucose, ketone, urobilinogen, bilirubin, red blood cells/erythrocytes, white blood cells (WBC)/leukocytes, pH, urine sediment (microscopic examination will be only performed in the event of abnormalities).

Urine pregnancy: Urine pregnancy testing will be conducted locally at the visits specified in the Schedule of Assessments.

7.1.3. Electrocardiograms

ECGs will be collected at baseline and at the EOS visit only unless clinically indicated.

7.1.4. Assessment of Cardiovascular Events

Information on CV events such as CHD death, major coronary events, and stroke will be collected as AE data.

7.1.5. Anti-ALN-PCSSC Antibodies

Additional sample for analysis of the induction of antibodies will be collected at the time points in the Schedule of Assessments ([Table 3](#)).

Aliquots of serum samples will be obtained and frozen, to permit future analysis of the effect of ALN-PCSSC on the expression of these exploratory biomarkers. Biological samples for biomarker research will be retained on behalf of the Sponsor for a maximum of 15 years following the last subject's last visit in the study. Details regarding the collection, processing, storage, and shipping will be in the Study Laboratory Manual.

7.2. Assessment of Efficacy

Specimens will be obtained at the time points in the Schedule of Assessments ([Table 3](#)). Subjects will be in a fasted state for all efficacy laboratory assessments. Parameters to be assessed will include: total cholesterol, triglycerides, LDL-C, HDL-C, non-HDL-C, VLDL-C, Apo-A1, Apo-B), Lp(a), hsCRP, and PCSK9.

7.2.1. Change from Baseline LDL-C

The primary efficacy endpoint is the percentage change in LDL-C from baseline to Day 180.

In addition, this study will assess:

- Percentage change in LDL-C from baseline to Day 90
- Percentage change in LDL-C from baseline to Days 14, 30, 60, 104, 120, 150, and 210
- Proportion of subjects in each group with LDL-C greater than 80% of the baseline value at Day 180 and Day 210
- Duration of time on treatment for subjects to return to 80% of baseline or greater LDL-C or PCSK9 protein
- Individual responsiveness defined as the number of subjects reaching on treatment LDL-C levels of <25 mg/dL, <50 mg/dL, 70 mg/dL, and <100 mg/dL at Days 90, 120, and 180
- Proportion of subjects in each group with greater or equal to 50% LDL-C reduction from baseline at Days 90, 120, and 180

Blood samples for determination of LDL-C (β -quantification) concentrations will be collected at the time points in the Schedule of Assessments. Details regarding the collection, processing, shipping, and storage of the samples will be provided in a Laboratory Manual.

7.2.2. Change from Baseline in Lipids/Lipoproteins

Secondary efficacy assessments will include the measure the effects of ALN-PCSSC on levels of lipids and lipoproteins including total cholesterol, triglycerides, LDL-C, HDL-C, non-HDL-C, VLDL-C, Apo-A1, Apo-B, Lp(a), hsCRP, and PCSK9.

- Percentage change in PCSK9 levels from baseline to Days 14, 30, 60, 90, 104, 120, 150, 180, and 210
- Percentage change in other lipids, and apolipoproteins from baseline at each subsequent visit to Day 210
- Proportion of subjects in each group who attain global lipid modification targets for their level of ASCVD risk

Additional aliquots of plasma and serum will be collected at each time point and stored for additional analyses, including future analysis of biomarkers of CV risk.

Plasma samples will be analyzed using a validated enzyme linked immunosorbent assay to determine PCSK9 protein concentration. Full details of the analytical methods used will be described in a separate bioanalytical report.

